10. ETHICAL AND REGULATORY REQUIREMENTS

10.1 Ethical conduct of the study

The study will be performed in accordance with ethical principles that have their origin in the Declaration of Helsinki and are consistent with International Conference on Harmonization (ICH)/Good Clinical Practice (GCP), applicable regulatory requirements and the AstraZeneca policy on Bioethics and Human Biological Samples.

10.2 Subject data protection

The ICF will incorporate (or, in some cases, be accompanied by a separate document incorporating) wording that complies with relevant data protection and privacy legislation.

10.3 Ethics and regulatory review

An Ethics Committee (EC) should approve the final study protocol, including the final version of the ICF and any other written information and/or materials to be provided to the patients. The investigator will ensure the distribution of these documents to the applicable EC, and to the study site staff.

The opinion of the EC should be given in writing. The investigator should submit the written approval to AstraZeneca before enrollment of any patient into the study.

The EC should approve all advertising used to recruit patients for the study.

AstraZeneca or designee should approve any modifications to the ICF that are needed to meet local requirements.

If required by local regulations, the protocol should be re-approved by the EC annually.

Before enrollment of any patient into the study, the final study protocol, including the final version of the ICF, is approved by the national regulatory authority or a notification to the national regulatory authority is done, according to local regulations.

AstraZeneca or designee will handle the distribution of any of these documents to the national regulatory authorities.

AstraZeneca or designee will provide Regulatory Authorities, ECs and Principal Investigators with safety updates/reports according to local requirements.

Each Principal Investigator is responsible for providing the EC/Institutional Review Board (IRB) with reports of any serious and unexpected adverse drug reactions from any other study conducted with the investigational product. AstraZeneca will provide this information to the Principal Investigator so that he/she can meet these reporting requirements.

10.4 Informed consent

The Principal Investigator(s) at each center will:

- Ensure each patient is given full and adequate oral and written information about the nature, purpose, possible risk, and benefit of the study
- Ensure each patient is notified that they are free to discontinue from the study at any time
- Ensure that each patient is given the opportunity to ask questions and allowed time to consider the information provided
- Ensure each patient provides signed and dated informed consent before conducting any procedure specifically for the study
- Ensure the original, signed ICF(s) is/are stored in the Investigator's Study File
- Ensure a copy of the signed ICF is given to the patient
- Ensure that any incentives for patients who participate in the study as well as any provisions for patients harmed as a consequence of study participation are described in the informed consent form that is approved by an EC.

10.5 Changes to the protocol and informed consent form

Study procedures will not be changed without the mutual agreement of the International Co-ordinating Investigator and AstraZeneca.

If there are any substantial changes to the study protocol, then these changes will be documented in a study protocol amendment and where required in a new version of the study protocol (Revised CSP).

The amendment is to be approved by the relevant EC and if applicable, also the national regulatory authority approval, before implementation. Local requirements are to be followed for revised protocols.

AstraZeneca will distribute any subsequent amendments and new versions of the protocol to each Principal Investigator(s). For distribution to EC, see Section 10.3.

If a protocol amendment requires a change to a center's ICF, AstraZeneca and the center's EC are to approve the revised ICF before the revised form is used.

If local regulations require, any administrative change will be communicated to or approved by each EC.

As a result of Protocol Amendment 3 (31 August 2015), all participating patients at the time of amendment approval will be asked to review and sign a revised ICF that describes the added Extension Period 2 that increases the duration of the study. If a patient does not consent to participate in Extension Period 2, the ICF should still be signed indicating the patient's preference not to continue receiving study drug but the patient will continue to participate in applicable visits and procedures.

10.6 Audits and inspections

Authorized representatives of AstraZeneca, a regulatory authority, or an EC may perform audits or inspections at the center, including source data verification. The purpose of an audit or inspection is to systematically and independently examine all study-related activities and documents, to determine whether these activities were conducted, and data were recorded, analyzed, and accurately reported according to the protocol, GCP, guidelines of the ICH, and any applicable regulatory requirements. The investigator will contact AstraZeneca or representative immediately if contacted by a regulatory agency about an inspection at the center.

Appendix B
Additional Safety Information

FURTHER GUIDANCE ON THE DEFINITION OF A SERIOUS ADVERSE EVENT (SAE)

Life threatening

‘Life-threatening’ means that the subject was at immediate risk of death from the AE as it occurred or it is suspected that use or continued use of the product would result in the subject’s death. ‘Life-threatening’ does not mean that had an AE occurred in a more severe form it might have caused death (eg, hepatitis that resolved without hepatic failure).

Hospitalization

Outpatient treatment in an emergency room is not in itself a serious AE, although the reasons for it may be (eg, bronchospasm, laryngeal edema). Hospital admissions and/or surgical operations planned before or during a study are not considered AEs if the illness or disease existed before the subject was enrolled in the study, provided that it did not deteriorate in an unexpected way during the study.

Important medical event or medical intervention

Medical and scientific judgement should be exercised in deciding whether a case is serious in situations where important medical events may not be immediately life threatening or result in death, hospitalisation, disability or incapacity but may jeopardize the subject or may require medical intervention to prevent one or more outcomes listed in the definition of serious. These should usually be considered as serious.

Simply stopping the suspect drug does not mean that it is an important medical event; medical judgement must be used.

Examples of such events are:

- Angioedema not severe enough to require intubation but requiring iv hydrocortisone treatment
- Hepatotoxicity caused by paracetamol (acetaminophen) overdose requiring treatment with N-acetylcysteine
- Intensive treatment in an emergency room or at home for allergic bronchospasm
- Blood dyscrasias (eg, neutropenia or anaemia requiring blood transfusion, etc) or convulsions that do not result in hospitalisation
- Development of drug dependency or drug abuse.

A GUIDE TO INTERPRETING THE CAUSALITY QUESTION

When making an assessment of causality consider the following factors when deciding if there is a ‘reasonable possibility’ that an AE may have been caused by the drug.

- Time Course. Exposure to suspect drug. Has the subject actually received the suspect drug? Did the AE occur in a reasonable temporal relationship to the administration of the suspect drug?
- Consistency with known drug profile. Was the AE consistent with the previous knowledge of the suspect drug (pharmacology and toxicology) or drugs of the same pharmacological class? OR could the AE be anticipated from its pharmacological properties?
- Dechallenge experience. Did the AE resolve or improve on stopping or reducing the dose of the suspect drug?
- No alternative cause. The AE cannot be reasonably explained by another etiology such as the underlying disease, other drugs, other host or environmental factors.
- Rechallenge experience. Did the AE reoccur if the suspected drug was reintroduced after having been stopped? AstraZeneca would not normally recommend or support a rechallenge.
- Laboratory tests. A specific laboratory investigation (if performed) has confirmed the relationship.

In difficult cases, other factors could be considered such as:

- Is this a recognized feature of overdose of the drug?
- Is there a known mechanism?

Causality of ‘related’ is made if following a review of the relevant data, there is evidence for a ‘reasonable possibility’ of a causal relationship for the individual case. The expression ‘reasonable possibility’ of a causal relationship is meant to convey, in general, that there are facts (evidence) or arguments to suggest a causal relationship.

The causality assessment is performed based on the available data including enough information to make an informed judgment. With limited or insufficient information in the case, it is likely that the event(s) will be assessed as ‘not related’.

Causal relationship in cases where the disease under study has deteriorated due to lack of effect should be classified as no reasonable possibility.

Clinical Study Protocol Appendix C

Drug Substance	Exenatide
Study Code	D5553C00003
Edition Number	1.0
Date	11 July 2014

Appendix C
Algorithm on Management of Sustained Elevated Liver Safety
Abnormalities

ALGORITHM ON MANAGEMENT OF SUSTAINED ELEVATED LIVER SAFETY ABNORMALITIES

The monitoring for liver safety will be performed using the serum levels of AST, ALT and TB (see [Figure 1](#) algorithm flow chart).

Patients with a central laboratory ALT and/or AST >3X ULN will be scheduled for a follow-up visit within 3 days following receipt of the initial laboratory results, to obtain repeat central laboratory ALT, AST, TB and Alkaline Phosphatase (ALK-P). In the event that the repeat laboratory assessments cannot be obtained within 3 days, the Investigator is encouraged to discuss possible alternatives with the Sponsor. Patients should remain on study medication until confirmatory results are obtained, unless otherwise contraindicated.

- **If the repeat ALT and AST are $\leq 3X$ ULN**, patient should continue double-blind treatment according to their original visit schedule unless otherwise contraindicated.
- **If the repeat ALT and/or AST are $>3X$ ULN but $\leq 8X$ ULN and TB $\leq 1.5X$ ULN**, the patient's medical history, including details of risk factors for liver diseases, should be evaluated for potential underlying aetiologies. In addition, specialized blood sampling will be performed to evaluate liver function as well as identify potential causes of laboratory elevation(s). The Investigator should continue to monitor the patient's liver tests every 3 days following receipt of the prior laboratory results until the ALT and AST are $\leq 2X$ ULN or until ALT and AST are at or below baseline levels. The frequency of retesting can decrease to once a week or less if abnormalities stabilize and the patient is asymptomatic. Patients should remain on study medication unless confirmatory results indicate that a criterion for discontinuation has been met or continuing study medication would be otherwise contraindicated.

Patients must be discontinued from the study if an initial and repeat confirmatory laboratory tests meet any of the following criteria:

- ALT and/or AST are $>3x$ ULN and TB $>2x$ ULN
- ALT and/or AST are $>5x$ ULN for ≥ 14 consecutive days, at any time after initial confirmatory results
- ALT and/or AST are $>8x$ ULN

In each of these situations, study medication will be discontinued, the Sponsor notified and the End of Treatment Visit performed within 3 days of the confirmed laboratory results (see [Section 3.9](#)). At the End of Treatment Visit, medical history including details of risk factors for liver diseases (if not previously assessed) will be requested and additional blood sampling performed (**Specialized Liver Panel** and **Liver Discontinuation Panel**, see detailed below). Patient should also be scheduled for a Follow-up Visit (ie, procedures of Visit 12) 3 weeks

after discontinuation of investigational product. A referral consultation to a hepatologist or gastroenterologist (specializing in liver abnormalities) should be obtained.

Any additional tests and/or examinations should be carried out at the discretion of the Investigator. Any further investigations and laboratory results for patients with abnormal laboratory values at the Follow-up Visit should be made available to the Sponsor upon request.

Additional information, including but not limited to completion of supplemental eCRFs may be requested for certain adverse events and/or laboratory abnormalities which are reported/identified as part of the hepatic safety surveillance.

Following the End of Treatment Visit, the Investigator should continue to monitor the subject's liver tests every 3 days following receipt of the prior laboratory results until the ALT and AST are $\leq 2x$ ULN or until ALT and AST are at or below baseline levels. The frequency of retesting can decrease to once a week or less if abnormalities stabilize and the subject is asymptomatic.

Guidance on Assessment of Hepatic Laboratory Abnormalities

The following is presented to assist in the evaluation and management of hepatic laboratory values. It is not intended to supplant Investigators' clinical judgment.

Patients who experience ALT and/or AST values $>3x$ ULN confirmed with a repeated test will have the following performed within 3 days of the confirmed laboratory results:

- AE assessment
- Physical Examination for jaundice and other signs of liver diseases
- Review of relevant risk factors and current history focusing on possible causes of the increased ALT and/or AST and/or TB, including:
 - Use of suspect concomitant medication [including over-the-counter (ie, acetaminophen/paracetamol), herbal and vitamin preparations]
 - Recent alcohol consumption or recreational drug/narcotic use
 - Recent unaccustomed physical exertion
 - Occupational or environmental exposure to hepatotoxins
 - Other conditions which may cause liver diseases or which may cause abnormal test results
- Specialized Liver Laboratory Panel (see below)

Specialized Liver Panel

For patients who are being monitored frequently as a result of confirmed AST and/or ALT >3x ULN, additional central laboratory tests will be performed within 3 days of receipt of confirmatory results. These laboratory tests will study the possible causes of the increased ALT and/or AST and/or TB, and may include, but are not limited to, the following tests:

- Hepatitis A IgM
- Hepatitis BsAg
- Hepatitis B Core Ab IgM
- Hepatitis C virus RNA
- Hepatitis C Ab
- Hepatitis E IgM
- Epstein-Barr Virus (EBV) IgM Ab
- Lactate Dehydrogenase (LDH)
- Gamma-glutamyl-transpeptidase (GGT)
- Carbohydrate deficient transferrin (CDT)
- Prothrombin time (PT/INR)
- Iron Panel - iron, ferritin, total iron binding capacity (TIBC)
- Immunology Panel including Antinuclear Antibody (ANA), Anti-Smooth Muscle Antibody (SMA) and Anti-Liver/Kidney Microsomal Antibody (Anti-LKM)
- Anti-tissue Transglutaminase Antibody

Liver Discontinuation Panel

[figure not shown]
For patients who are discontinued from the study as a result of sustained elevated liver safety abnormalities, additional central laboratory tests will be performed at the time of End of Treatment Visit. Similar to the Specialized Liver Panel, these laboratory tests will study the possible causes of the increased ALT and/or AST and/or TB, and may include, but are not limited to, the following tests:

- Cytomegalovirus (CMV) IgM Ab
- Herpes Simplex Virus (HSV) 1 and 2

- Ceruloplasmin
- Toxoplasmosis
- Alpha-1 antitrypsin

For specific details regarding the Specialized Liver Panel or the Liver Discontinuation Panel laboratory tests, refer to the Central Laboratory Manual for this study.

Figure 1 Sustained elevated liver safety abnormalities flow chart

^a In patients with repeat ALT or AST > 3x ULN but ≤ 8x ULN, only patients with TB ≤ 2x ULN at Step 1 should be followed according to Step 2b. Patients with an initial TB and confirmatory repeat TB > 2x ULN should be followed according to Step 2d.

^b Please see text above in the Appendix for details on additional assessments to be performed (AE assessment, PE, review of current medical history including focused review of current medical history including focused review of risk factors for liver diseases and collection of blood samples [specialized liver panel or liver discontinuation panel]).

^c Confirmatory repeat AST, ALT, ALK-P and TB should be obtained every 3 days following receipt of prior laboratory results, until the ALT and AST are ≤ 2x ULN or until ALT and AST are at or below baseline levels. The frequency of retesting can decrease to once a week or less if abnormalities stabilize and the patient is asymptomatic.

Clinical Study Protocol Appendix D

Drug Substance	Exenatide
Study Code	D5553C00003
Edition Number	1.0
Date	11 July 2014

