3.9 Discontinuation of investigational product

Patients may be discontinued from the study medication in the following situations:

- Patient decision. The patient is at any time free to discontinue treatment, without prejudice to further treatment.
- Patient experiences an AE that, in the investigator's opinion, necessitates discontinuation from study medication.
- The investigator decides that the patient should discontinue study medication. If this decision is made because of a serious adverse event (SAE) or a clinically significant abnormal laboratory value, appropriate measures are to be taken. The Sponsor or its designee is to be alerted immediately. Refer to Section 6.4, Reporting of SAEs.
- Severe non-compliance with the study protocol.
- Calculated creatinine clearance <45 mL/min confirmed by repeat testing or a decrease in renal function that would preclude continued treatment with metformin according to local guidance.
- Loss of glucose control. If any patient experiences a loss of glucose control, in addition to study medication, the investigator should initiate rescue therapy and the patient may continue study participation. The

investigator should follow local prescribing information for the rescue therapy and may discuss appropriate rescue therapy with the AstraZeneca Medical Monitor if needed. Patients must first complete the Rescue visit procedures before receiving open-label rescue therapy. Rescued patients with central laboratory HbA1c values $>8.0\%$ despite a maximum tolerated dose of rescue therapy for 12 weeks will be discontinued from the study and referred for additional anti-hyperglycemic therapy (see Section 4.2).

- Patients with a central laboratory ALT and/or AST $>3x$ ULN will be scheduled for a follow-up visit within 3 days following the receipt of the result (see Appendix C, “Algorithm on Management of Sustained Elevated Liver Safety Abnormalities”). Patients should be discontinued from study medication if the initial and repeat laboratory tests meet any of the following criteria:
 - ALT and/or AST are $>3x$ ULN **and** TB $>2x$ ULN.
 - ALT and/or AST are $>5x$ ULN for ≥ 14 consecutive days, at any time after initial confirmatory results.
 - ALT and /or AST are $>8x$ ULN.

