3.9.1 Procedures for discontinuation of a patient from investigational product

If deemed necessary by the investigator, study medication can be stopped temporarily and then re-started after discussion with the medical monitor. These situations will be handled on a case by case basis and all decisions will be documented in the patient’s study file.

At any time, patients are free to discontinue study medication or withdraw from the study (ie, study medication and assessments – see Section 3.10), without prejudice to further treatment. A patient that decides to discontinue study medication will always be asked about the reason(s) and the presence of any AEs. AEs will be followed up (see Section 6); patient diaries and all study medications should be returned by the patient.

Patients who discontinue permanently from the study medication will have an Early Termination Visit equivalent to the Week 28 assessments at the time of study medication discontinuation (see Section 4.2.2). Discontinued patients will then be contacted via telephone according to the visit schedule in the Study Plan (Table 1 and Table 2), ie, during the time windows during which the scheduled clinic visits would have been conducted. At these contacts, the following data will be collected and entered onto the clinical database:

- Concomitant medication
- AEs

Discontinued patients should return to the study site and complete assessments required for Visit 12 (Week 28), Visit 15 (Week 52), and Visit 19 (Week 104) as appropriate and outlined in the Study Plan ([Table 1](#) and [Table 2](#)). These patients will also be contacted via telephone according to the visit schedule in the Study Plan ([Table 1](#) and [Table 2](#)).

Discontinued patients should also return to the study site to complete the Follow-up visit (Visit 20) 10 weeks after the Visit 19 (Week 104) assessments.

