6.3.7 Hy’s Law

Cases where a patient shows an AST or ALT > 3x ULN together with total bilirubin > 2x ULN must be reported as SAEs.

Potential Hy's Law cases that meet any of the identification criteria specified in Appendix C will require an unscheduled laboratory draw for assessment by the central laboratory (see central laboratory manual for further instructions on appropriate laboratory kit).

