6.8.2 Hepatic Adjudication Committee

An independent Hepatic Adjudication Committee, blinded to the treatment of the patients, will determine the probability that drug-induced liver injury (DILI) is the cause of liver-related abnormalities, including, but not limited to:

- Hepatic events timely related to death (within 30 days before death)
- AST and/or ALT >3x ULN and TB >2x ULN (within 14 days of the AST and/or ALT elevation)

- AST and/or ALT >10 x ULN

A separate Adjudication Manual will define and describe the procedure for the handling, reporting and classification of these cases.

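### The mandatory liver stop needs both the initial and the repeat sample to qualify, so bilirubin first passing 2x ULN on the repeat requires no stop or hold on those two samples

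*Protocol*

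**What the plan says.** Two places in the protocol set the liver stopping rule. Section 3.9 says: "Patients should be discontinued from study medication if the initial and repeat laboratory tests meet any of the following criteria". Appendix C is firmer: "Patients must be discontinued from the study if an initial and repeat confirmatory laboratory tests meet any of the following criteria". Both list the same three criteria: ALT and/or AST above 3x ULN with TB above 2x ULN; ALT and/or AST above 5x ULN for at least 14 consecutive days; ALT and/or AST above 8x ULN.

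The second sentence of footnote a to the Appendix C flow chart carries the two-sample condition over to bilirubin: "Patients with an initial TB and confirmatory repeat TB > 2x ULN should be followed according to Step 2d". Its first sentence reserves Step 2b, among patients whose repeat ALT or AST is above 3x and up to 8x ULN, for those with TB at most 2x ULN at Step 1.

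On dosing before the repeat is known, Appendix C says: "Patients should remain on study medication until confirmatory results are obtained, unless otherwise contraindicated". Section 3.9.1 allows a temporary stop: "If deemed necessary by the investigator, study medication can be stopped temporarily and then re-started after discussion with the medical monitor".

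Elsewhere the combined elevation is acted on without a second qualifying sample. Section 6.3.7 says: "Cases where a patient shows an AST or ALT > 3x ULN together with total bilirubin > 2x ULN must be reported as SAEs". Section 6.2 also treats it as serious, and Section 6.8.2 sends it for blinded adjudication when the TB rise falls within 14 days of the ALT/AST rise.

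**The concern.** Bilirubin may rise after the transaminases. The protocol allows for this order, since adjudication accepts a TB value up to 14 days from the ALT/AST elevation. Yet when TB first crosses 2x ULN on the repeat sample, the stopping rule looks back to an initial sample that did not qualify, and nothing obliges anyone to stop or hold study drug.

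What is at stake is further dosing, by discretion, in a patient whose result the protocol already classes as an SAE. The weekly injection matters most here. Section 1.1 describes gradual release of exenatide from microspheres, so a dose given in that interval cannot be withdrawn in the way a daily tablet can be stopped.

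**Working it through.** No sample size, power or alpha figure is involved. The check sets one case against each rule.

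**Case.** Initial sample: ALT/AST above 3x and up to 8x ULN, TB at most 2x ULN. Repeat sample: ALT/AST above 3x and up to 8x ULN, TB above 2x ULN.

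**Stopping criteria (Section 3.9 and Appendix C).**

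| Criterion | Initial | Repeat | Met on both? |
|---|---|---|---|
| ALT/AST >3x with TB >2x | No (TB ≤2x) | Yes | No |
| ALT/AST >5x for ≥14 days | Cannot be shown | Cannot be shown by two samples a few days apart | No |
| ALT/AST >8x | No | No | No |

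The rule could mean that the same criterion must be met twice, or that each sample must meet some criterion. The initial sample meets none, so the stop is not triggered under either reading. It would be triggered only if the repeat alone were enough, which the wording does not allow. Had TB been above 2x on both samples, the stop would apply.

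**Other branches in the Appendix C text.** The return to normal follow-up needs repeat ALT and AST at or below 3x ULN; this patient is above. The monitoring branch needs TB at or below 1.5x ULN; this patient is above 2x. Neither fits.

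**Footnote a.** Step 2d needs TB above 2x on both samples, so it does not apply. Step 2b is tied to TB at Step 1, which was at most 2x, so the footnote may route the patient there. The content of Step 2b is not visible.

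**Hold.** The remain-on-drug default runs only until the confirmatory result. After that, the temporary stop in Section 3.9.1 is available but depends on the investigator's judgement. Sections 6.2, 6.3.7 and 6.8.2 attach reporting and adjudication to the value, not a stop or hold.

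**Length of the discretionary interval.** Footnote c gives the retest timing: "Confirmatory repeat AST, ALT, ALK-P and TB should be obtained every 3 days following receipt of prior laboratory results". So:

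- interval = 3 days + laboratory turnaround;
- the protocol does not state turnaround; assuming 0 to 3 days gives 3 + 0 = 3 to 3 + 3 = 6 days;
- that is 3 to 6 daily tablets and, because 6 days is less than 7, at most 1 weekly injection, and only if nobody stops the drug.

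The documents give no basis for how often this sequence would occur, so no frequency is claimed.

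**The case against.** The strongest reply is that this is a confirmation rule working as intended. The algorithm is titled for sustained abnormalities, and a permanent stop on one bilirubin value could rest on a spurious result. Thresholds for reporting and adjudication can properly be lower than the threshold for a permanent stop, so a reader who infers that Sections 6.3.7 and 6.8.2 contradict Section 3.9 goes too far. That part of the reply stands, and confirmation before permanent discontinuation should be kept.

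The safeguards are also substantial:

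- SAE notice to the sponsor within 24 hours (Section 6.4);
- an unscheduled draw for potential Hy's Law cases that meet Appendix C's identification criteria (Section 6.3.7);
- medical monitor contact (Section 5.2.5.3);
- work-up within 3 days of the confirmed result (Appendix C);
- permanent or temporary stopping at the investigator's discretion (Sections 3.9 and 3.9.1).

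If the next retest again shows ALT/AST above 3x with TB above 2x ULN, two samples then meet the criterion. The effect is a delay of about one retest. This stands too, but none of these safeguards requires drug to be withheld in the meantime.

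A reader might infer that the text gives this patient no route at all, neither stopping nor continuing drug. The documents do not support that, because footnote a can be read as sending the patient to Step 2b. If Step 2b is the monitoring branch, the patient stays on drug. On either reading, no mandatory stop or hold follows from the visible text.

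It may also be argued that Appendix C keeps patients on drug only until confirmatory results show a discontinuation criterion, so the repeat could suffice. That sentence belongs to the branch with TB at or below 1.5x ULN, and the criteria it points to are themselves tied to both tests.

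**Conclusion.** The point holds in a narrow form. With ALT/AST above 3x and up to 8x ULN on both samples and TB first above 2x ULN on the repeat, the protocol requires neither a stop nor a hold on those two samples. Dosing until the next retest is left to the investigator.

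The effect is about one retest interval: nominally 3 days from receipt of the repeat result, or 3 to 6 days if turnaround is 0 to 3 days. Few patients are expected and no efficacy endpoint is touched. It is a low-priority safety clarification, worth making because it is cheap.

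The conclusion rests on the wording of Section 3.9, Appendix C and the flow-chart footnotes; the flow chart itself is not visible. For that reason the point should not be stretched to a first ALT/AST value above 8x ULN on the repeat. A reader might infer the same gap there from the body text, but the flow chart may cover it. The point is also separate from the difference between the 1.5x bilirubin limit in the Appendix C text and the 2x limit in footnote a: raising the former to 2x would still leave TB above 2x on the repeat uncovered.

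**What to change.** In Section 3.9, Appendix C and footnote a, add that once ALT/AST above 3x ULN is confirmed, any repeat or later sample first showing ALT/AST above 3x with TB above 2x ULN requires:

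- both study drugs, including the next weekly injection, to be held under Section 3.9.1;
- a retest within 3 days;
- permanent discontinuation if the retest confirms the finding.

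Sections 6.3.7 and 6.8.2 need no change.

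The cost is one or two sentences in each place. The change uses the existing temporary-stop mechanism, adds no scheduled visit, and can be made together with aligning the 1.5x and 2x bilirubin limits. The downside is an occasional short hold on a value that is not confirmed.
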